Table 2. Schedule of activities for Treatment Period 2 of Study I7P-MC-DSAD For procedures at an early termination visit, see ETV in Table 2. For procedures at an unscheduled visit, see V997 in Table 2. Unscheduled visits are for participants needing rescue therapy or incision and drainage. V11 V12 V14 V17 V19 **V20** ETV V997 Visit number V13 V15 V16 V18 Comment Week from randomization 22 24 26 28 34 36 18 20 30 32 127 141 155 169 183 197 211 225 239 253 Study day Visit interval tolerance ± 2 (days) X **Fasting visit** Patient Global Impression of Χ X X Change – 7 Days (Hidradenitis Suppurativa) **Patient-Reported Outcomes (Paper)** X Spinal Pain NRS X See Section 8.1.8. **Clinician-Administered Questionnaires (Electronic)** X X Includes anatomical region, type Lesion assessments X X X X X X X X X X and number (see Section 8.1.1). Clinician-Administered Questionnaires (Paper) X X X X X C-SSRS Since Last Visit X X X X X X X Self-Harm Supplement X X X X X X X X X X X X Form Self-Harm Follow-Up Form X X X X X X X X X X Required if triggered by the X X Self-Harm Supplement Form per instructions. **Laboratory Tests and Sample Collections** Hematology X X X X \mathbf{X} X X X X X Χ X X X X X X X X Clinical chemistry X X X

Table 2. Schedule of activities for Treatment Period 2 of Study I7P-MC-DSAD

For procedures at an early termination visit, see ETV in Table 2.

For procedures at an unscheduled visit, see V997 in Table 2. Unscheduled visits are for participants needing rescue therapy or incision and drainage.

For procedures at an unschedu		ĺ											
Visit number	V11	V12	V13	V14	V15	V16	V17	V18	V19	V20	ETV	V997	Comment
Week from randomization	18	20	22	24	26	28	30	32	34	36	—	_	
Study day	127	141	155	169	183	197	211	225	239	253			
Visit interval tolerance													
(days)	±2	±2	±2	±2	±2	±2	±2	±2	±2	±2	—	_	
Fasting visit										X			
Lipid panel										X	X		Participants should not eat or drink
													anything but water for 12 hours
													before the visit. Fasting is not
													required at an ETV. If a participant
													attends these visits in a nonfasting
													state, the sample should still be
													collected. This will not be
													considered a protocol violation.
Urinalysis										X	X		•
Urine pregnancy (local)	X	X	X	X	X	X	X	X	X	X	X		Only for WOCBP (Section 8.2.5.1,
, ,													Appendix 10.4) and women with a
													history of tubal ligation. Result

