Table 3. Schedule of activities for the Post-Treatment Follow-Up Period of Study I7P-MC-DSAD For procedures at an early termination visit, see ETV in Table 2. For procedures at an unscheduled visit, see V997 in Table 2. Unscheduled visits are only for participants needing rescue therapy or incision and drainage. V802 Visit number V801 **Comment** 40 or 46 or Week relative to randomization ETV+4 ETV+10 323 Study day 281 Visit interval tolerance (days) ±7 ±7 Fasting visit No fasting in this period. X Concomitant medications X X X For AESIs, additional data are collected (Section 8.3.6). Adverse events Surgical interventions related to HS X X **Physical Evaluation** Blood pressure, body temperature, pulse rate. Vital signs should be measured after X X participant has been sitting for at least 5 minutes. Vital signs Symptom-directed physical examination X X See Section 8.2.2. **Patient-Reported Outcomes (Electronic)** Skin Pain - HS NRS X X X X Drainage NRS X Smell NRS X Patient's Global Impression of Severity – X 7 Days (Hidradenitis Suppurativa) X **Patient-Reported Outcomes (Paper)** Spinal Pain NRS Χ See Section 8.1.8. **Clinician-Administered Questionnaires (Electronic)** Lesion assessments Χ Χ Includes anatomical region, type and number (see Section 8.1.1). Clinician-Administered Questionnaires (Paper) C-SSRS Since Last Visit X X Self-Harm Supplement Form X X Χ Self-Harm Follow-Up Form Χ Required if triggered by the Self-Harm Supplement Form per instructions. **Laboratory Tests and Sample Collections** Hematology X X

X

X

Clinical chemistry

Table 3. Schedule of activities for the Post-Treatment Follow-Up Period of Study I7P-MC-DSAD

For procedures at an early termination visit, see ETV in Table 2.

For procedures at an unscheduled visit, see V997 in Table 2. Unscheduled visits are only for participants needing rescue therapy or incision and drainage.

Visit number	V801	V802	Comment
	40 or	46 or	
Week relative to randomization	ETV+4	ETV+10	
Study day	281	323	
Visit interval tolerance (days)	±7	±7	
Fasting visit			No fasting in this period.
			Only for WOCBP (Section 8.2.5.1 and Appendix 10.4) and women with a history of
Urine pregnancy (local)	X	X	tubal ligation.
C-reactive protein, high-sensitivity (hs-CRP)		X	
			If a hypersensitivity event occurs, collect additional samples (see Appendix 10.2,
Pharmacokinetic (PK) sample X		X	Section 10.2.2).
			If a hypersensitivity event occurs, collect additional samples (see Appendix 10.2,

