4.1. Overall Design

Study I7P-MC-DSAD (DSAD) is a multicenter, randomized, double-blind, placebo-controlled, parallel-group Phase 2 study to evaluate the efficacy and safety of LY3041658 600 mg given intravenously (IV) every 2 weeks (Q2W) in adults with HS.

The study duration will be up to approximately 51 weeks over 4 study periods:

Screening: a period lasting up to 35 days before Week 0 (Visit 2, baseline)

Treatment Period 1: a 16-week, 2-group double-blind treatment period:

• At baseline (Visit 2, Week 0), eligible participants will be randomized in a 2:1 ratio to receive either LY3041658 600 mg IV Q2W or placebo IV Q2W, starting at the baseline visit.

Treatment Period 2: a 20-week, single-group open-label extension period:

• Starting at Week 16, all participants, including those previously assigned to placebo, will receive LY3041658 600 mg IV Q2W until the last dosing visit.

Post-treatment follow-up: a period lasting approximately 10 weeks.

- Participants will not receive study drug in this period.
- The last dose of study drug is given at Visit 19 (Week 34). Thus, participants will have been withdrawn from study drug for a total of 12 weeks at the last post-treatment follow-up visit (Visit 802, Week 46).

The study schema is presented in Section 1.2.

Unscheduled visits are for participants needing rescue therapy or incision and drainage. The use of concomitant medications, including rescue therapy, is described in Section 6.5.

Participants who permanently discontinue the study drug early (Section 7.1) will undergo early termination procedures, including an early termination visit (ETV) and the post-treatment follow-up visits specified in the Schedule of Activities (SoA) (Section 1.3).

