4.2. Scientific Rationale for Study Design

The primary endpoint of this study is the proportion of patients achieving Hidradenitis Suppurativa Clinical Response (HiSCR) at Week 16. HiSCR is defined as at least a 50% reduction in the total abscess and inflammatory nodule count (AN count) with no increase in abscess count and no increase in draining fistulae count relative to baseline. HiSCR has been used in previous HS trials and has been accepted by the Food and Drug Administration as a primary endpoint (Kimball et al. 2014; Kimball et al. 2016a; Kimball et al. 2016b). Evaluation of the primary endpoint at the Week 16 time point is appropriate based on current clinical trials of systemic immunomodulatory therapies in HS (guselkumab NCT03628924, secukinumab NCT03713632 and NCT03713619; bimekizumab NCT04242498 and NCT04242446).

A double-blind, placebo-controlled design through the first treatment period limits bias for the participant and investigator assessments and enables a clearer interpretation of the effects of active drug.

The second treatment period (open-label) allows for evaluation of both safety and changes in efficacy over time in participants who received LY3041658 in the placebo-controlled treatment period. The second treatment period also allows participants who were randomized to placebo in the first treatment period to receive LY3041658 in the open-label period for a treatment duration similar to that of the placebo-controlled period.

The post-treatment follow-up period allows for continued safety monitoring after the last dose. The last dose is given at Week 34. This is 2 weeks before the last visit in the second treatment period (Week 36) and a total of 12 weeks before the last post-treatment follow-up visit (Week 46). LY3041658 concentrations are expected to be significantly decreased in the plasma after 5 half-lives. The terminal half-life of LY3041658 is approximately 2 weeks, based on pharmacokinetic (PK) data from the Phase 1 Study DSAB. Therefore, for the present study, the planned duration of safety follow-up is adequate, as this duration covers approximately 6 half-lives. A follow-up period of a similar duration was used after the last dose of LY3041658 in the single-dose Study DSAA and multiple-dose Study DSAB.

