## 5. Study Design

### 5.1. Summary of Study Design

Study I7P-MC-DSAD (DSAD) is a multicenter, randomized, double-blind, placebo-controlled, parallel-group Phase 2 study to evaluate the efficacy and safety of LY3041658 600 mg given intravenously (IV) every 2 weeks (Q2W) in adults with HS.

The study duration will be up to approximately 51 weeks over 4 study periods:

Screening: a period lasting up to 35 days before Week 0 (Visit 2, baseline)

Treatment Period 1: a 16-week, 2-group double-blind treatment period:

- At baseline (Visit 2, Week 0), eligible participants will be randomized in a 2:1 ratio to receive either LY3041658 600 mg IV Q2W or placebo IV Q2W, starting at the baseline visit.

Treatment Period 2: a 20-week, single-group open-label extension period:

- Starting at Week 16, all participants, including those previously assigned to placebo, will receive LY3041658 600 mg IV Q2W until the last dosing visit.

Post-treatment follow-up: a period lasting approximately 10 weeks.

- Participants will not receive study drug in this period.
- The last dose of the study drug is given at Visit 19 (Week 34). Thus, participants will have been withdrawn from study drug for a total of 12 weeks at the last post-treatment follow-up visit (Visit 802, Week 46).

Approximately 76 patients will be screened to achieve approximately 51 participants randomized in a 2:1 ratio to one of two treatment groups:

[figure not shown]
approximately 34 participants randomized to LY3041658, and

approximately 17 participants randomized to placebo.

Unscheduled visits are for participants needing rescue therapy or incision and drainage. The use of concomitant medications, including rescue therapy, is described in Section 6.5 in the protocol.

Participants who permanently discontinue the study drug early (Section 7.1 in the protocol) will undergo early termination procedures, including an early termination visit (ETV) and the post-treatment follow-up visits specified in the Schedule of Activities (SoA) (Section 1.3 in the protocol).

Figure DSAD.5.1 illustrates the study design. The blinding procedure is described in the protocol.

**Figure DSAD.5.1. Schema of Study I7P-MC-DSAD, a Phase 2 study to evaluate the efficacy and safety of LY3041658 in adults with moderate-to-severe hidradenitis suppurativa.**

Note: Starting at Week 16 participants who received placebo in Treatment Period 1 will receive LY3041658 600 mg IV Q2W.

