### **6.9. Safety Analyses**

The general methods used to summarize safety data, including the definitions of baseline values, are described in Section 6.3.2.

Safety analyses will include data after rescue unless otherwise stated, and patients will be analyzed according to the investigational product to which they were randomized at Week 0 (Visit 2). Additional analyses may be conducted using data after rescue to systemic therapy for some safety topics such as systemic treatment-emergent adverse events (TEAEs), and serious adverse events (SAEs). Safety analyses will take place using the safety population defined in Section 6.3.1.

Safety topics that will be addressed include the following: AEs, clinical laboratory evaluations, vital signs and physical characteristics.

Unless otherwise specified, by-visit summaries will include planned on-treatment visits. For tables that summarize events (such as AEs, categorical lab abnormalities, shift to maximum value), post-last dose follow-up data will be provided for Treatment Period 1 (Week 0 to Week 16) and Treatment Period 2 (Week 16 to Week 36) separately. For deaths and malignancies, all

available follow-up data up to the end of the study will be included. Listings will include all safety data.

For selected safety assessments, descriptive statistics may be presented for the last measure observed during post-treatment follow-up (up to 30 days after the last dose of treatment including rescue, regardless of the study period).

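### For completers without rescue after Visit 19, the 30-day limit in SAP 6.9 leaves out both scheduled post-treatment follow-up visits

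*SAP*

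**What the plan says.** SAP 6.9 sets out how safety data after treatment are handled. One sentence deals with follow-up measurements: "For selected safety assessments, descriptive statistics may be presented for the last measure observed during post-treatment follow-up". A parenthesis in that sentence limits it to "up to 30 days after the last dose of treatment including rescue, regardless of the study period".

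The same section confines by-visit summaries to planned on-treatment visits unless stated otherwise. It uses all follow-up data for deaths and malignancies, and puts every safety observation in the listings. SAP 6.9.3 takes the last laboratory observation from the dosing period.

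Protocol 4.1 and SAP 5.1 both name post-treatment follow-up as a study period of about 10 weeks after Treatment Period 2, and both put the last dose at Visit 19 (Week 34). Protocol 4.2 says of that dose: "This is 2 weeks before the last visit in the second treatment period (Week 36) and a total of 12 weeks before the last" follow-up visit. It defends the length of follow-up on the ground that "this duration covers approximately 6 half-lives". Protocol 1.3, Table 3, schedules vital signs, hematology and clinical chemistry at both V801 and V802.

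**The concern.** The summary is described as coming from post-treatment follow-up, yet the window attached to it closes before a completer's first visit in that period. The only scheduled visit that a completer can contribute is V20, the last visit of Treatment Period 2.

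At stake is a usable summary of off-drug measurements. The protocol runs follow-up for 12 weeks so that safety can be observed while drug concentrations fall. Continuous laboratory and vital-sign values are collected twice in that time. This sentence is the one place in SAP 6.9 that expressly provides descriptive statistics for them.

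**Working it through.** **Inputs**
- Protocol 1.3, Table 2: Visit 19 (last dose) Day 239 ±2; V20 Day 253 ±2, no dosing.
- Protocol 1.3, Table 3: V801 Day 281 ±7, or the early termination visit (ETV) plus 4 weeks; V802 Day 323 ±7, or ETV plus 10 weeks.
- SAP 6.9: window of 30 days after the last dose, including rescue.
- Protocol 4.2: terminal half-life about 2 weeks.
- Not given: L, the days from last dose to ETV in early discontinuers. It is varied from 0 to 16 as an assumption.

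**1. The protocol's own figures.** Last dose to V802: 323 − 239 = 84 days = 12 weeks. Last dose to V20: 253 − 239 = 14 days = 2 weeks. Half-lives covered: 84 / 14 = 6. All three are reproduced.

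**2. Completers, counted from the last study-drug dose.** Nominal gap = visit day − 239. Minimum = (visit day − tolerance) − (239 + 2). Maximum = (visit day + tolerance) − (239 − 2).

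| Visit | Nominal | Minimum | Maximum | Within 30 days? |
|---|---|---|---|---|
| V20 | 14 | 251 − 241 = 10 | 255 − 237 = 18 | always |
| V801 | 42 | 274 − 241 = 33 | 288 − 237 = 51 | never |
| V802 | 84 | 316 − 241 = 75 | 330 − 237 = 93 | never |

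The window closes on Day 239 + 30 = 269, or on Day 271 if Visit 19 is two days late. The earliest V801 is Day 274.

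**3. Early discontinuers.** V801 falls L + 28 ± 7 days after the last dose.

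| L (days) | V801, days after last dose | Can be within 30 days? |
|---|---|---|
| 0 | 21 to 35 | yes |
| 7 | 28 to 42 | yes, if early in tolerance |
| 9 | 30 to 44 | only at the earliest day |
| 10 | 31 to 45 | no |
| 14 | 35 to 49 | no |

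The condition is L + 21 ≤ 30, so L ≤ 9. How many people this concerns is uncertain. Protocol 9.2 expects about 45 of 63 to complete Treatment Period 1, so 63 − 45 = 18 (29%) do not. SAP 6.2 still has 51 randomized, which gives 51 − 45 = 6 (12%).

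**4. Late rescue.** Protocol 6.5.3 allows rescue during the study, and Table 3 foresees unscheduled rescue visits in follow-up. V801 is inside the window if rescue is given on or after its day minus 30: Day 281 − 30 = 251 for a nominal V801, with a range of 274 − 30 = 244 to 288 − 30 = 258 across its tolerance.

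**5. Time off drug.** Thirty days is 30 / 14 = 2.1 half-lives. On simple first-order decline about 0.5^2.14 = 23% of drug remains then, against 0.5^6 = 1.6% at 12 weeks. V20, at one half-life, is earlier still.

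**The case against.** A reader might infer that the summary would hold no follow-up visit at all. The documents do not support that. An early discontinuer's V801 is timed from the ETV and can fall inside 30 days, and late rescue restarts the clock even for a completer.

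A reader might also infer that using V20 would mislabel on-treatment data. The SAP states that the window applies whatever the study period, and V20 is a visit without dosing two weeks after the last dose, so the text permits it.

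A third inference would be that 12 weeks of off-drug safety data go unsummarized. That too goes beyond the documents. Listings carry everything, deaths and malignancies use all follow-up, and Protocol 9.4.5 summarizes follow-up-emergent adverse events. SAP 6.9 also promises post-last-dose data in event tables, including categorical laboratory abnormalities. Its period wording there (Weeks 0 to 16 and 16 to 36) leaves it unclear whether V801 and V802 count.

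Finally, the sentence is permissive, covers selected assessments and takes only the last value. No test or required output depends on it, and the half-life argument justifies how long people are followed, not a particular table.

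All of this stands and narrows the point. It does not remove the mismatch for completers without late rescue. The exceptions also create a further problem: most completers would contribute V20, while some early discontinuers and late-rescued participants would contribute V801. Time off drug would then vary with disposition and rescue use under a single label.

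**Conclusion.** The point holds in a limited form and is minor. For completers without rescue after Visit 19, 0 of 2 scheduled follow-up visits can fall inside the 30-day window, and the shortfall is at least 33 − 30 = 3 days even at the most favorable tolerances. If the optional summary is produced, it would use V20 for most completers and V801 for a few others. Continuous laboratory and vital-sign values at V801 and V802 would have no descriptive summary for these completers.

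This assumes that visits stay within tolerance and that the Visit 19 dose was given (if it was missed, the gap is longer). It also assumes that the SAP 6.9 default of on-treatment visits governs the by-visit displays in SAP 6.9.3, which refer to each visit from randomization without naming the follow-up visits. The size of the mixing cannot be stated, because the documents give neither L nor the frequency of late rescue.

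**What to change.** In SAP 6.9, replace the 30-day limit with a window defined by study period and anchored to the last study-drug dose: all data after the last treatment-period visit or the ETV, through V802. Summarize V801, V802 and the last follow-up value.

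If a day count is kept, it must be at least 93 days for completers. Adding the 7-day tolerance to 12 weeks gives 84 + 7 = 91 days, which would still miss an in-tolerance V802 at 93. A definition by period avoids this and also suits early discontinuers, whose visits are timed from the ETV.

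The data are already scheduled for collection, and nothing in the conduct of the trial changes. The cost is a short SAP edit and a small additional descriptive display.

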### **6.9.1. Extent of Exposure**

Duration of exposure (in days) to study drug will be summarized for the safety population in both Period 1 and 2 by treatment group using descriptive statistics (n, mean, SD, minimum, 1st quartile, median, 3rd quartile, maximum).

For subjects without drug interruption, the duration of exposure for each patient is the date of last dose – date of first dose +1. If subjects have drug interruption, the duration of exposure for each patient is the (Treatment end date before drug interruption – date of first dose +1) + (date of last dose – treatment re-start date +1).

### **6.9.2. Adverse Events**

Adverse events are recorded in the eCRFs. Each AE will be coded to system organ class (SOC) and preferred term (PT) using the Medical Dictionary for Regulatory Activities (MedDRA) version that is current at the time of database lock. Severity of AEs is recorded as mild, moderate, or severe.

A TEAE is defined as an event that either first occurred or worsened in severity after the first dose of study treatment and on or prior to the last visit date during the analysis period. For each event classification term, the number of participants experiencing a TEAE with that classification term will be tabulated. TEAEs will be summarized by treatment period and overall for the study.

Treatment-related TEAEs are defined as events that are indicated by the investigator on the eCRF to be related to treatment. For events that are gender-specific, the denominator and computation of the percentage will include only participants from the given gender.

Adverse events are classified based upon the MedDRA PT. The MedDRA Lowest Level Term (LLT) will be used in defining which events are treatment-emergent. The maximum severity for each LLT during the baseline period up to the first dose of the study medication will be used as the baseline. If an event with missing severity is preexisting during the baseline period, and persists during the treatment period, then the baseline severity will be considered mild for determining TEAE (that is, the event is treatment-emergent if the severity is coded moderate or severe postbaseline and not treatment-emergent if the severity is coded mild postbaseline). If an event occurring postbaseline has a missing severity rating, then the event is considered treatment-emergent. The day and time for events where onset is on the day of the first dose of study treatment will both be used to distinguish between pretreatment and posttreatment in order to derive treatment-emergence. Should there be insufficient data for AE start date to make this

comparison (for example, the AE start year is the same as the treatment start year, but the AE start month and day are missing), the AE will be considered treatment-emergent.

In an overview table, the number and percentage of subjects who experienced a TEAE or serious adverse event (SAE), died due to an AE, or discontinued from the study due to an AE will be summarized by treatment.

The frequency and percentages of patients with TEAEs will be summarized by treatment using MedDRA PT nested within SOC. Events will be ordered by decreasing frequency within SOC. The frequency and percentages of patients with TEAEs by maximum severity will also be summarized by treatment using MedDRA PT nested within SOC.

Fisher's exact test will be performed to compare percentages for each LY3041658 dose group and Placebo at both the SOC and PT levels.

Listings will be presented for all AEs, all SAEs, all AEs leading to death, all AEs leading to study drug temporary interruption, and all AEs leading to discontinuation from the study.

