9.4.5. Safety Analyses

Safety analyses will include adverse events, SAEs, AESIs, C-SSRS, vital signs, ECGs, and laboratory analytes, using the Safety Population data descriptively summarized by treatment group. Categorical safety measures will be summarized with incidence rates. Continuous safety measures will be summarized as mean change by visit. Exposure to study intervention will be calculated for each participant and summarized by treatment group.

Adverse events will be coded according to the *Medical Dictionary for Regulatory Activities* (MedDRA) and summarized by system organ class (SOC), preferred term, severity, and

relationship to the study intervention. A treatment-emergent adverse event (TEAE) is defined as an event that first occurred or worsened in severity after baseline, with baseline defined as all pre-existing conditions recorded at Visit 1 and any adverse events recorded before the first dose of study intervention (that is, during the interval between Visits 1 and 2 and recorded with the time of onset before the first dose of study intervention). The treatment periods will be used as the postbaseline period for the analysis. Safety analyses will be conducted separately for each treatment period. For events that are gender specific, the denominator and computation of the percentage will include only participants from the given gender.

The number and percentage of participants who experienced TEAEs, TEAEs by maximum severity, deaths, SAEs, TEAEs related to study intervention, discontinuations from the treatment due to an adverse event, and AESIs will be summarized. Treatment-emergent adverse events (all, by maximum severity), SAEs including deaths, and adverse events that lead to treatment discontinuation will be summarized and analyzed by MedDRA SOC and preferred term.

Treatment-related TEAEs (TEAEs related to study intervention) are defined as events that are indicated by the investigator on the eCRF to be related to treatment.

Adverse events of special interest will be identified by a standardized MedDRA query (SMQ) or a Lilly-defined MedDRA preferred term listing.

Suicide-related thoughts and behaviors occurring during treatment will be summarized based on responses to the C-SSRS consistent with the C-SSRS Scoring and Data Analysis Guide (Columbia Lighthouse Project WWW).

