In this protocol, the term "participant" is used to indicate an individual who participates in a clinical trial, either as a recipient of an investigational medicinal product or as a control. This usage reflects preferences indicated by patient advocates to more

accurately reflect the role of people who take part in clinical trials.

PD pharmacodynamics

PK pharmacokinetics

PK/PD pharmacokinetics/pharmacodynamics

PPD purified protein derivative

PRO/ePRO patient-reported outcomes/electronic patient-reported outcomes

Q2W every 2 weeks

QTc corrected QT interval

RNA ribonucleic acid

SAE serious adverse event

SAP statistical analysis plan

screen The act of determining if an individual meets minimum requirements to become part of

a pool of potential candidates for participation in a clinical study.

SoA Schedule of Activities

study drug See "study intervention"

study intervention Any investigational intervention, marketed product, placebo, or medical device

intended to be administered to a study participant according to the study protocol

TB tuberculosis

TBL total bilirubin level

TE treatment emergent

TEAE Treatment-emergent adverse event: An untoward medical occurrence that emerges

during a defined treatment period, having been absent pretreatment, or worsens relative to the pretreatment state, and does not necessarily have to have a causal relationship

with this treatment.

TST tuberculin skin test

ULN upper limit of normal

USA United States of America; also United States

WBC white blood cell

WOCBP women of childbearing potential (see Appendix 10.4, Section 10.4.1.)

xN non-inflammatory nodules, when used in the context of lesion counts

11. References

A study to evaluate the efficacy, safety, and tolerability of guselkumab for the treatment of participants with moderate to severe hidradenitis suppurativa (HS) (NOVA). ClinicalTrials.gov website. https://clinicaltrials.gov/ct2/show/NCT03628924. Updated January 22, 2020. Accessed February 13, 2020.

- A study of efficacy and safety of two secukinumab dose regimens in subjects with moderate to severe hidradenitis suppurativa (HS) (SUNRISE). ClinicalTrials.gov website. https://clinicaltrials.gov/ct2/show/NCT03713632. Updated February 6, 2020. Accessed February 13, 2020.

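### SAP 6.9.2 gives adverse events no Period 2 baseline and no lower time limit, so an event that began on placebo can be counted again as treatment-emergent after the Week 16 switch to LY3041658

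*SAP*

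**What the plan says.** SAP 6.9.2 defines emergence as follows: "A TEAE is defined as an event that either first occurred or worsened in severity after the first dose of study treatment". The sentence goes on to close the window: "on or prior to the last visit date during the analysis period". The severity comparator is the maximum for each MedDRA Lowest Level Term (LLT) "during the baseline period up to the first dose of the study medication will be used as the baseline". On reporting, the section says "TEAEs will be summarized by treatment period and overall for the study".

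Protocol 9.4.5 uses the same kind of baseline: conditions recorded at Visit 1 plus "any adverse events recorded before the first dose of study intervention". It adds: "The treatment periods will be used as the postbaseline period for the analysis". The protocol glossary (Appendix 7) describes a TEAE as emerging "during a defined treatment period, having been absent pretreatment, or worsens relative to the pretreatment state".

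Three other places bear on the point:

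- SAP 6.3.2 sets a Period 2 baseline at the last value before Visit 10, and the opening of SAP 6.9 refers to 6.3.2 for baseline definitions.
- SAP 6.9 analyses safety by the product randomized at Week 0, whereas the Safety population in SAP 6.3.1 and protocol 9.3 groups participants by what they received in each period.
- SAP 5.1 has every participant, former placebo participants included, on LY3041658 from Week 16.

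**The concern.** For a placebo-randomized participant, the first dose of study treatment is a placebo infusion at Week 0, and first exposure to LY3041658 comes 16 weeks later. A Period 2 table should show what emerged after that exposure. The SAP's event rule does not refer to the Week 16 dose. Its window closes at the end of the analysis period but does not open at the start of it, and its severity comparator stays at the state before Week 0. Nor does it say whether an event belongs to a period by onset, by worsening or by being present.

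The Period 2 table is the planned tabulated summary of first exposure in the former placebo group. If placebo-onset events enter it, the rate on LY3041658 is overstated and a new signal is harder to see. Infections matter most: they are an event of special interest (protocol 8.3.6) and were the most common kind of TEAE in the earlier multiple-dose study (protocol 2.3).

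**Working it through.** The plan states no figure on this point, so there is none to reproduce.

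**Step 1: apply the possible rules to test events.** Each event is in a placebo-randomized participant. The question is whether it counts as a Period 2 TEAE.

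| Test event | SAP wording as written | Present in Period 2, pre-Week 0 baseline | Onset in Period 2, pre-Week 0 baseline | Baseline = state at the Visit 10 dose |
|---|---|---|---|---|
| A. Mild, starts Week 10, continues unchanged | yes | yes | no | no |
| B. Mild, starts Week 10, resolves Week 12 | yes | no | no | no |
| C. Mild, starts Week 10, becomes moderate in Period 2 | yes | yes | no | yes |
| D. Mild episode resolved in Period 1, new mild episode Week 20 | yes | yes | yes | yes |
| E. First ever episode, mild, Week 20 | yes | yes | yes | yes |
| F. Mild before Week 0, moderate in Period 1, still moderate in Period 2 | yes | yes | no | no |

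Events A and F carry over under two of the three readings that keep the pre-Week 0 baseline. Event B carries over only if the missing lower limit is taken literally. Assignment by onset date alone removes A, B and F, but it also drops C, which worsened on LY3041658.

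A baseline equal to the maximum severity over all of Period 1 would handle A, B, C and F like the last column but would exclude D, a new episode on LY3041658.

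**Step 2: the day of Visit 10.** SAP 6.9 gives the windows as Weeks 0 to 16 and Weeks 16 to 36. Visit 10 ends the first window and carries the first Period 2 dose. The date-and-time rule in SAP 6.9.2 covers only the day of the first study dose, so nothing separates events before and after the infusion at Visit 10.

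**Step 3: scale.** Inputs: about 45 participants expected to complete 16 weeks (protocol 9.2, SAP 6.2); placebo 21 of 63 in the protocol and 17 of 51 in the SAP. With dropout proportional across arms:

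- Switchers: 45 × 21/63 = 15, and 45 × 17/51 = 15.
- One carried-over participant among switchers: 1/15 = 6.7 percentage points.
- One carried-over participant among all 45 in Period 2: 1/45 = 2.2 points.

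These are the full effect for a given preferred term. In the row for any TEAE, a participant who also has a genuinely new Period 2 event adds nothing.

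**Step 4: how many might carry over.** The documents give no rate. Assume 5% to 30% of switchers have a placebo-onset event ongoing at Week 16:

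- Expected number: 15 × 0.05 = 0.75 to 15 × 0.30 = 4.5.
- Share of the pooled 45: 0.75/45 = 1.7% to 4.5/45 = 10%.
- Chance of at least one: 1 − 0.95^15 = 54% to 1 − 0.70^15 = over 99%.

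**The case against.** The strongest reply is that the literal reading is not what anyone would program. It would put event B, which was over by Week 12, into the Period 2 table. Protocol 9.4.5 makes each treatment period the post-baseline period, the glossary speaks of emergence within a defined period, and SAP 6.9 separates the two windows. Together these favour assignment by onset, under which a placebo-onset event stays in Period 1. This stands in part: the double count is permitted by the SAP, not prescribed. But the SAP, which governs the derivation, states no assignment rule, and onset alone would lose event C.

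A second reply is that SAP 6.9 points to 6.3.2, which does have a Period 2 baseline. That baseline is worded for measured values. SAP 6.9.2 then gives events their own LLT rule and does not reset it.

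A third is that the event need not appear under LY3041658 at all. Grouping by arm randomized (SAP 6.9) keeps switchers in the placebo-randomized column, and the Period 2 columns would then already be the two sequences. That is correct, but SAP 6.3.1 says the opposite, so the column is undetermined.

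Finally, the stakes are bounded. Listings cover all adverse events, so nothing is hidden from case review, and Period 2 is open-label with no concurrent placebo group.

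**Conclusion.** As written, SAP 6.9.2 allows an adverse event that began on placebo to be counted again as treatment-emergent in Period 2. The cause is a stated rule, a pre-Week 0 baseline with no lower time limit, applied to a table it does not fit.

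A reader might infer that the plan does count placebo events as emergent on LY3041658. The documents do not support that: the protocol wording leans towards onset, and the two grouping rules conflict. A reader might also put rates on the literal reading; for example, 60% with a Period 1 event and an independent 50% with a new one would give 1 − 0.4 × 0.5 = 80% in place of 50%. The documents give no such rates and independence is doubtful: with full overlap the same inputs give 60%. No figure of that kind should be relied on.

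The supportable size is 6.7 points among switchers, or 2.2 points pooled, for each carried-over participant, with 0.75 to 4.5 participants affected. This rests on proportional dropout, on completers entering Period 2, and on the assumed 5% to 30%. Carry-over can only add to the Period 2 counts and does not affect the randomized Period 1 comparison. The change should be made before the Period 2 tables are programmed.

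**What to change.** In SAP 6.9.2:

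- Define a Period 2 TEAE as an event with onset after the Visit 10 dose, or an event ongoing at that dose that worsens beyond its severity at that dose. Use date and time for events on the day of Visit 10.
- Count a new-onset recurrence of an event that resolved in Period 1, and flag it as a recurrence, so that repeat infections on LY3041658 are not hidden.
- Keep the Week 0 baseline for the Period 1 and overall tables.
- Present Period 2 by sequence: placebo to LY3041658, and LY3041658 to LY3041658.
- Reconcile the grouping rule in SAP 6.9 (arm randomized) with that in SAP 6.3.1 (treatment received in each period).

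The cost is one SAP paragraph, a period-specific derivation flag and a recurrence flag. Events continuing unchanged from Period 1 leave the Period 2 table but remain in the Period 1 and overall tables and in the listings. The Period 2 comparator (state at the dose) will differ from the Period 1 comparator (maximum LLT severity before the dose), so a footnote should say that the two periods' rates are not defined identically.
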